5.8 Multi-centre Studies

Individual centre results will not be summarised. In doubt of underlying centre effects, they may be explored where deemed appropriate or necessary.

6 Summary of Study Data

Progression-free survival (PFS), overall survival (OS), and other time-to-event data will be analysed using the Kaplan-Meier method, the Cox's proportional Hazard model (for hazard ratio computation) and the Log-rank test (stratified for the main analysis, non-stratified on randomization factors where needed for sensitivity analysis).

For OS, the main analysis will take into consideration new anti-cancer treatment starts and/or treatment switches if a high proportion ($\geq 33\%$) of patients in the control arm started new anti-cancer treatment or received subsequent PRRT treatment. In this case the main OS analysis would be conducted treating treatment as time-dependent variable and sensitivity analyses

would include Rank preserving structural failure time (RPSFT), Intent To Treat and censoring at time of switch.

Cox proportional hazard regression will also be used when adjusting for the co-variables

- primary tumour origin (GE-NET vs. P-NET),
- prior medical treatment (1st line vs. 2nd line),
- tumour grade (G1 vs. G2)
- baseline KPS (70, 80, 90 and 100),

The same covariates can be used for subgroup analyses as deemed appropriate and necessary. Other baseline characteristics such as but not limited to:

- Age (continuous or <65 vs. ≥65 or <75 vs. ≥75)
- Gender (M vs. F)
- Ethnic origin (White/Caucasian vs. others)
- ECOG (recalculated: 1=KPS 70 or 80 vs. 0=KPS 90 or 100)
- Time from primary diagnosis (continuous in months)
- Time from diagnosis of progression (continuous in months)
- Chromogranin A at baseline (continuous or >2*ULN vs. ≤2*ULN)
- Alkaline Phosphatase at baseline (continuous or >ULN vs. ≤ULN)
- BMI (continuous or ≤21 vs. 22 to 27 vs. >27)
- P-NET functioning status
- site of metastases (e.g. extra-hepatic vs. no extra-hepatic)
- Received SSA prior to baseline
- Received SSA prior to baseline and continue during treatment period

etc.

can also be used for subgroup analysis and/or Cox proportional Hazard regression with stepwise approach as deemed appropriate.

For time-to-event endpoint (PFS, OS), the proportional hazard assumption will be examined using appropriate method(s) including graphical diagnostics and/or statistical tests where needed.

In case of unequivocal non-proportional hazards (e.g. crossing survival curves), the main time-to-event analysis can be rather based on Restricted Mean Survival Time (RMST) approach in addition to Log-rank and Cox model. Alternatively, this approach can be used as sensitivity analysis to further investigate the results patterns where deemed appropriate.

The unstratified RMST analysis will be used if there is at least one strata with either:

- 1) too few participants to comparatively analyse;
- 2) no participant followed up for long enough to make a proper comparison

Continuous parameters:

Will be summarized using standard summary statistics as appropriate (n, mean, standard deviation, minimum, 25th percentile, median, 75th percentile and maximum). Corresponding 95% CIs may be presented where meaningful.

Ordinal and categorical variables:

Summary statistics will include

- frequency counts and percentages.
- corresponding 95% confidence interval may be presented where meaningful.

Non-parametric methods will be used for comparison between study groups or subgroups (Mann-Whitney U test), changes within groups (Wilcoxon test) or percentages (Chi² test/Fisher's exact test).

Statistical tests will be stratified for the main analyses (e.g. stratified log-rank test for time to event comparisons, Mantel Haenszel test for percentage comparisons) but appropriate corresponding non-stratified tests can be used where deemed necessary for sensitivity analysis purposes.

[figure not shown]
Other variables will be analysed descriptively or by means of frequency tables.

All data of the clinical database will be listed, summaries will be provided for at least the primary and secondary efficacy endpoints and for the safety endpoints.

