Everolimus: Patients randomised to everolimus therapy will undergo out-patient visits only. Patients will receive a standard dose of 10 mg daily, which may be reduced, where required for acceptable tolerability, according to manufacturer's product information (see [Appendix 4](#)).

Both study arms: Study visits will be monthly in the first 12 months, thereafter 3-monthly until end of study at month 30 or until progression (whatever occurs first). For symptom control, all patients are allowed to receive somatostatin analogues (SSA), as clinically indicated (best supportive care) in required doses, not to exceed licensed doses. In the  $^{177}\text{Lu}$ -edotreotide arm, clinically established wash-out periods prior to  $^{177}\text{Lu}$ -edotreotide dosing have to be considered (1 day for immediate release, and 28 days for sustained release SSA).

Safety, tolerability and symptom control parameters, as well as tumour markers are captured at regular intervals.

To assess efficacy, serial morphological imaging, comprising native liver and contrast-enhanced liver and 3 regional (pelvis, abdomen, thorax) MRI or CT (see Clinical Imaging Manual for details), is scheduled every three months, consistently using baseline methods. Evaluation of tumour response will be performed by local investigators using RECIST 1.1 criteria.

In case of clinically suspected tumour progression, investigators may schedule appropriate diagnostic imaging at any time.

Image analyses will also be conducted centrally. For establishment of PFS (primary endpoint) blinded reading in duplicate, with adjudication in case of discordance will be used.

Patients who progressed under everolimus may be offered  $^{177}\text{Lu}$ -edotreotide therapy based on the personal judgement of the Investigator, if he/she considers it appropriate and likely to be beneficial for the individual patient (see Section [7.4.2](#)).

To further evaluate tumour response, the tumour marker Chromogranin A (Cg-A) will be determined at baseline, and then monthly until month 12, thereafter in 3-monthly intervals until diagnosis of progression or end of study. Cg-A represents a secretory protein present in dense-core vesicles of neuroendocrine (NE) cells. It is being expressed in most secretory, but also non-functional NET. Cg-A is the best circulating neuroendocrine marker available up to now for the management of differentiated

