- Patients on stable doses of SSA who develop exacerbation of symptoms due to clinical fluctuation of a hormone-release (e.g. carcinoid) syndrome during the study, may receive SSA rescue medication, as clinically appropriate, at the discretion of the investigator. Rescue medication type, dosing, duration, and clinical symptomatology will be recorded in detail. Such patients will remain in the study and receive further study treatments as scheduled. Subcutaneous, short-acting Somatostatin Analogue injections may be used as rescue medication, in accordance with the manufacturer's prescribing information.

Concomitant SSA use will be recorded throughout the study. Data of all patients receiving any SSA while on study will be statistically analysed for a possible impact on the primary endpoint (sensitivity analysis).

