5.4.4 Other Characteristics

Summary tables and/or listings will be provided for demographics and other baseline characteristics, including the above-mentioned variables and:

- Age, ethnic origin, sex, physical exam
- Medical/surgical history at baseline,
- Prior and concomitant medication
- Time from primary diagnosis, time from diagnosis of progression, number and type of prior therapies for condition, site(s) of metastases
- Histological entity, functional state
- HRQL scores at baseline (QLQ C30 and GI.NET21 questionnaires)
- Change of inclusion criteria (protocol version 2.2 amendment 2) based on record in CRF.

All variables of population characteristics will be confirmed by non-parametric statistical testing for both treatment groups to check their comparability at baseline (except for detailed physical examination, medications, and medical/surgical history). If there should be major differences between the treatment groups, their impact on the analysis will be investigated including with stratified methods if appropriate.

In addition, appropriate methods (stratification, multivariate analyses, subgroup analyses) will be used to assess the impact of patient characteristics, tumour histology and rescue SSA drugs on tumour response as foreseen in the exploratory study objectives.

Cox proportional hazard model will be used for PFS and OS to explore treatment effect within each subgroup. And forest plots (including p-value and 95 % confidence interval) of hazard ratios for PFS and OS will be presented. The pre-specified subgroups are:

- primary tumour origin (GE-NET vs. P-NET),
- prior medical treatment (1st line vs. 2nd line),
- tumour grade (G1 vs. G2) based on local assessment for baseline
- baseline KPS (70, 80, 90 and 100)
- Received SSA prior to baseline or not
- Received SSA prior to baseline and did not stop prior baseline
- Change of inclusion criteria (protocol version 2.2 amendment 2) based on record in CRF.

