5.6 Baseline Definition

Unless stated otherwise:

- for demographic parameters, tumour assessment, QoL, biomarkers and in general all efficacy related variables, baseline is defined as the last non-missing measurement on or prior to randomisation date.
- for lab, vital signs and in general all safety related variables, baseline is defined as the last non-missing measurement prior to first dosing of study treatment.

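### An SSA grouping that depends on continuation after randomisation is listed as a baseline characteristic, and no time-dependent or landmark method is named for on-study SSA

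*SAP*

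**What the plan says.** Four places in the documents deal with SSA as an explanatory factor.

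- **SAP Section 6.** A list introduced by "Other baseline characteristics such as but not limited to" includes "Received SSA prior to baseline and continue during treatment period". The items on it "can also be used for subgroup analysis and/or Cox proportional Hazard regression with stepwise approach as deemed appropriate".
- **SAP 5.4.4, pre-specified subgroups.** The corresponding item reads "Received SSA prior to baseline and did not stop prior baseline". It is settled by baseline.
- **SAP 5.4.4, rescue SSA.** Methods given as stratification, multivariate and subgroup analyses "will be used to assess the impact of patient characteristics, tumour histology and rescue SSA drugs on tumour response".
- **Protocol 6.1.2.** "Data of all patients receiving any SSA while on study will be statistically analysed for a possible impact on the primary endpoint (sensitivity analysis". No method is stated. Protocol 9.3.1 adds that concomitant SSA, as a baseline or intercurrent factor, will be examined by sensitivity analysis.

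For efficacy variables, SAP 5.6 says that "baseline is defined as the last non-missing measurement on or prior to randomisation date". Treating an exposure as time-dependent is mentioned in SAP Sections 6 and 7 only for new anticancer treatment and treatment switches, chiefly for OS. It is not mentioned for SSA.

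**The concern.** Whether a patient continues SSA during treatment, or receives rescue SSA, is learned after randomisation. Under Protocol 4.6 a patient's study participation ends at progression, and under Protocol 8.1.3 concomitant medication is recorded until the end-of-study visit. On-study SSA can therefore be recorded only while the patient is still on study. Someone who progresses early has little chance to enter the SSA group. If membership is treated as a fixed label from day 0, SSA users are credited with progression-free time that they had to survive in order to qualify.

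Membership may also depend on arm. Protocol 3.1 requires "clinically established wash-out periods prior to" dosing in the 177Lu-edotreotide arm (28 days for sustained-release SSA), with no counterpart for everolimus. A treatment comparison inside a group defined by on-study SSA is then no longer a randomised comparison.

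At stake is the promised check on whether concomitant SSA affects the PFS result, together with the exploratory SSA analyses of response.

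**Working it through.** **Inputs from the documents.** Median PFS 11 vs 17 months, so HR = 11/17 = 0.6471; 180 events; 100 and 200 patients; two-sided 5%; 15% dropout (SAP Section 4). Follow-up 30 months (SAP 3.4.1). Scans every 3 months from month 3 (Protocol 8.2.1.2).

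**Assumptions.** The documents give no rate of SSA use. Start rates of 0.5-4% per month, and a 20% share of continuing users, are assumed.

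**1. The plan's own figure.** Schoenfeld power with d = 180, p = 1/3, |ln 0.6471| = 0.4353: √(180 × 1/3 × 2/3) × 0.4353 − 1.96 = 6.325 × 0.4353 − 1.96 = 0.793, and Φ(0.793) = 78.6%. The SAP states 80%, so the PFS assumptions are a sound base.

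**2. Why the bias arises.** Take exponential PFS with hazard λ, SSA started at rate r with no effect, and no censoring. Never-users have mean PFS 1/(r+λ); ever-users have 1/(r+λ) + 1/λ. The ever/never rate ratio is therefore λ/(2λ + r), which is below 0.5 for any r > 0. With λ = ln 2/17 = 0.0408 and r = 0.01, this is 0.0408/0.0916 = 0.45; with λ = ln 2/11 = 0.0630, it is 0.0630/0.1360 = 0.46.

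**3. SSA newly started on study, fixed ever/never coding.** Simulation of 100 + 200 patients with the inputs above, true SSA HR = 1, Cox model stratified by arm, 400 trials per setting:

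| Start rate per month | Ever-users | Apparent PFS HR | Trials falsely protective (p<0.05) |
|---|---|---|---|
| 0.5% | 8% | 0.54 | 57% |
| 1% | 14% | 0.52 | 89% |
| 2% | 26% | 0.49 | 99.5% |
| 4% | 43% | 0.43 | 100% |

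With exact event times instead of 3-monthly scans, the HR is 0.48-0.36, in line with step 2. With SSA as a time-dependent covariate in the same data, the HR is 0.98-1.00 and 2-5% of trials are significant.

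**4. The quoted item: prior users who continue (20% assumed), true HR = 1.** The SAP does not say when continuation must be shown.

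| Reading | Apparent HR |
|---|---|
| Ongoing at day 0 | 1.00 |
| Record needed after month 1 | 1.00 (0.92 with exact event times) |
| After month 3 | 0.80 |
| After month 6 | 0.66 |
| After month 9 | 0.54 (falsely protective in 83%) |
| Resumed after wash-out, mean delay 1 / 3 months | 0.98 / 0.90 |

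**5. Rescue SSA and response.** With illustrative response rates of about 4% (everolimus) and 12% (177Lu-edotreotide) and no SSA effect, the ever/never odds ratio for response is 1.3-1.7.

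**6. Treatment HR inside on-study SSA groups.** With equal start rates in both arms the distortion is small: 0.64-0.65 in ever-users and 0.69-0.73 in never-users, against 0.67-0.68 overall. If everolimus patients start SSA at 4% and 177Lu-edotreotide patients at 2% per month, the HR is 0.67 overall but 0.60 and 0.59 in the two groups. At 4% vs 1% it is 0.65 overall but 0.55 and 0.53. Both groups then overstate the treatment benefit.

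**7. Confounding by indication.** At a 1% start rate the crude ever/never rate ratio is 0.52 when starts are unrelated to prognosis. If half the patients have 4 times the hazard and 10 times the start rate, it becomes 0.98.

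**The case against.** A reader might infer that the quoted SAP item itself would make SSA look protective in most trials. The documents do not support that. The item covers prior users who carry on, not SSA started on study. Protocol 6.1.2 has non-functional patients who progressed under SSA stop before randomisation and lets functional pancreatic NET patients on a stable dose continue. Continuers should therefore mostly be identifiable on day 0, and on that reading there is no immortal time. The 57-100% false-positive rates belong to newly started SSA only.

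Nor do the documents prescribe ever/never coding throughout. Protocol 6.1.2 gives no method. Stratification appears in SAP 5.4.4 for rescue SSA and tumour response, not in SAP Section 6 and not for PFS. The Section 6 list is optional, while the pre-specified subgroup in SAP 5.4.4 already uses the baseline-fixed definition. The direction is not assured either: on-study SSA follows new or worsening hormonal symptoms, and step 7 shows that this can cancel the apparent benefit.

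All of this stands and limits the size of the point. It does not remove it. The Section 6 item still contradicts SAP 5.6. Rescue SSA is by nature given after randomisation, yet the methods named for it include fixed groupings. Two biases that happen to offset leave a result that cannot be interpreted.

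**Conclusion.** The point holds within limits. One listed baseline characteristic contains post-randomisation information and disagrees with the SAP's baseline rule and its own subgroup list. For SSA given on study, no method is named that handles the timing of exposure.

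The size depends on coding that the documents leave open. Fixed ever/never coding of newly started SSA produces a large spurious association with PFS and a smaller one with response. For the continuation item the bias ranges from nil to substantial according to when continuation is ascertained. These results assume the SAP's PFS medians, invented SSA use rates, illustrative response rates, and SSA starts unrelated to prognosis except in step 7.

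The confirmatory tests of PFS, ORR and OS do not use these variables. What is at risk is the exploratory and sensitivity evidence on SSA. The correction should be made before analysis because it is cheap and the present groupings depend on time on study.

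**What to change.** 1. In the SAP Section 6 list, replace the continuation item with SSA ongoing at randomisation, matching SAP 5.4.4.
2. State the method for the PFS analysis promised in Protocol 6.1.2: SSA given after randomisation enters the stratified Cox model as a time-dependent covariate, 0 before the first on-study dose and 1 from then on.
3. For rescue SSA and tumour response in SAP 5.4.4, use a landmark: classify SSA use up to a fixed time (for example month 3) among patients still at risk, and count response after it.
4. Do not present treatment effects within groups defined by on-study SSA as randomised comparisons.

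The cost is SAP wording and programming; Protocol 6.1 already has medication start and stop dates recorded. There are three downsides. The landmark analysis uses fewer patients. Time-dependent coding removes immortal time but not confounding by indication. SAP 5.5 imputes partial SSA dates to the start or end of the month or year, which may misplace some exposure.

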6.1 Subject Disposition

Patient assignment to the analysis sets, specified in the following, will be performed and listed prior to any analysis taking place.

Flow Diagram according to CONSORT 2010

6.2 Protocol Deviations

As per current protocol (see Protocol Section 9.3.2), for the study arms at least the following protocol deviations are defined as major protocol deviations which should lead to PP set exclusion

- ¹⁷⁷Lu-edotreotide arm:
 - Subjects with incomplete ¹⁷⁷Lu-edotreotide infusion, in which less than 50% of the total pre-scribed activity (GBq) based on initially dosimetry assessment was injected.
 - Subjects missing more than two scheduled doses, or in whom doses were administered more than 30 days outside the date, specified per protocol.
- Everolimus arm:
 - Subjects missing more than 14 doses, within a visit interval of 30 days (with exception of treatment interruptions due to toxicity (see protocol Section 5.4.2)).

Decisions on all Serious Protocol deviations which lead to PP set exclusion will be taken on an ongoing basis according to the Protocol Deviation Plan, confirmed at the blind data review meetings and finalised before analysis. Protocol deviations and the resulting exclusions from the PP set will be summarised and listed in a frequency distribution table.

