Safety, tolerability and symptom control parameters, as well as tumour markers are captured at regular intervals.

To assess efficacy, serial morphological imaging, comprising native liver and contrast-enhanced liver and 3-regional (pelvis, abdomen, thorax) MRI or CT (see Clinical Imaging Manual for details), is scheduled every three months, consistently using baseline methods. In case of clinically suspected tumour progression, investigators may

	
schedule appropriate diagnostic imaging at any time. Diagnosis of progression will be made by the local investigator.
 
All image analyses will be confirmed centrally. For establishment of PFS (primary endpoint) blinded reading in duplicate, with appropriate adjudication in case of discordance will be used.
 
Patients who progressed under everolimus may be offered Lu-edotreotide therapy based on the personal judgement of the Investigator, if he/she considers it appropriate and likely to be beneficial for the individual patient.

Study participation duration	
 
• Screening period: 90 days (day -90 to day -1)
 
• Study period: 
 
- Treatment period IMP: Four single doses administered on days 0, 90, 180 and 270, unless diagnosis of progression or EOS.
 
- Treatment period RP: Daily oral administration from day 0 until diagnosis of progression or EOS.
 
- Study period: day 0 – month 30 (or until diagnosis of progression, whichever is earlier).
 
 
 
• Post-study Follow-up (5 years [60 months] post-EOS): 
 
- Lu-edotreotide therapy for patients (having progressed under everolimus therapy): Administration and follow-up as for study patients, until secondary progression.
 
- All patients: Collection of overall survival (OS) and progression data, as well as information on further cancer treatments and the development of secondary malignancies.
 
 
 

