## 5.4 Dosage and Administration

### 5.4.1 Lu-edotreotide Group

Patients assigned to Lu-edotreotide treatment will undergo at most four cycles of  $7.5 \pm 0.7$  GBq Lu-edotreotide, each containing a mass dose of 150 µg edotreotide. The cumulative Lu-edotreotide dose will be up to 30 GBq with treatment cycles every 3 months.

Lu-edotreotide will be administered as a slow intravenous infusion over 10 – 20 min, via a flexible cannula into the cubital vein of the non-dominant arm (i.e. left arm in right-handers and vice versa). Concomitantly to the administration of Lu-edotreotide patients will receive a nephroprotective amino acid solution (starting 30 – 60 min before IMP, and lasting 4 - 6 h) as described in Section 6.1.3.

In most regulatory environments, Lu-edotreotide administration requires a short-term hospitalisation in a radionuclide therapy ward for radiation protection reasons, in order to minimise irradiation of others, and in order to collect radioactive excretions. During cycle 1 (D1), patients will undergo planar scintigraphy and SPECT/CT imaging (see Section 8.2.2), to determine the absorbed dose (AD) to kidneys and tumour from Lu-edotreotide from this first cycle (D1). AD to kidneys will be determined centrally by image core laboratory (ICL), to ensure methodological uniformity across all sites. Dosimetry prescription information will be returned to the sites by the central ICL in a timely manner, sufficiently in advance before the subsequent cycle.

Patients randomised to the Lu-edotreotide group experiencing progressive disease under treatment must stop study participation.

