As only standard  $^{177}\text{Lu}$ -edotreotide doses of  $7.5 \text{ GBq} \pm 0.7 \text{ GBq}$  are used in this study, dose modification will not be achieved by reducing the next planned dose, but by delaying the next treatment cycle up to a maximum of 4 weeks (week 16 (+ 2)). In such a situation, subsequent PRRT cycles and evaluations (except for evaluation of tumour response based on morphological imaging RECIST 1.1) will be performed in intervals of 90 ( $\pm 14$ ) days, calculated from the delayed PRRT cycle. In case toxicity has not recovered by week 16, a patient cannot receive further PRRT cycles, but will remain in the study.

Following the second occurrence of DMT, the patient is excluded from further treatment, but will remain in the study.

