## 5.7 Treatment Compliance

A record of the number of  $^{177}\text{Lu}$ -edotreotide doses and everolimus tablets dispensed to and taken by each subject must be maintained and reconciled with study treatment and compliance records. Details of each study drug administration will be recorded in appropriate source documents and then reported in the CRF.

- $^{177}\text{Lu}$ -edotreotide:

$^{177}\text{Lu}$ -edotreotide will be administered by study personnel at the trial site only. In any case of interruption of  $^{177}\text{Lu}$ -edotreotide infusion, the infused and discarded amounts will be recorded.  $^{177}\text{Lu}$ -edotreotide is to be ordered on the day of randomisation. The first dose of  $^{177}\text{Lu}$ -edotreotide should be administered within 21 days of randomisation. In case of any delay, the site should check with the Sponsor via the site monitor and the reason for delay should be documented accordingly.

- Everolimus:

Subjects will be asked to maintain a dosing diary to record their daily administration of everolimus. At each visit, the subject should return the dosing diary. An evaluation of subject compliance with study treatments taken will be performed. The investigator will make every effort to bring non-compliant subjects into compliance. Compliance with dosing will be assessed through querying the subject during site visits and will be documented in the source documents and in the CRF, including treatment start and stop dates, dates for treatment delays and/or dose reductions.

The following deviations are defined as major protocol deviations, leading to exclusion from the PP set (see Section 9.3.3):

- $^{177}\text{Lu}$ -edotreotide arm:

- Subjects with incomplete  $^{177}\text{Lu}$ -edotreotide infusion, in which less than 50% of the total pre-scribed activity (GBq) based on initially dosimetry assessment was injected.
- Subjects in whom a dose was administered more than 30 days outside the per protocol date.

- Everolimus arm:
  - Subjects missing more than 14 doses, within a visit interval of 30 days (with exception of treatment interruptions due to toxicity, see Section 5.4.3.1).

Regardless whether a patient is compliant or non-compliant, the investigator must make every effort to perform all investigations according to the protocol for the entire duration of study participation.

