#### **9.3.3.2 Per Protocol set (PP)**

In order to determine if any bias results from including untreated patients or patients lost to follow-up in the primary FAS analysis, an additional analysis will be conducted on patients who are protocol-compliant: the Per Protocol set (PPS). Patients with major protocol violations determined before statistical analysis will be excluded from this population. Major protocol violations are defined as those that could impact the efficacy or safety evaluations and will be specified in the SAP. For the study arms the following deviations are defined as major protocol deviations, leading to exclusion from the PPS:

- Lu-edotreotide arm:
  - Subjects with incomplete Lu-edotreotide infusion, in which less than 50% of the total pre-scribed activity (GBq) based on initially dosimetry assessment was injected.
  - Subjects missing more than two scheduled doses, or in whom dose were administered more than 30 days outside the date, specified per protocol.
- Everolimus arm:
  - Subjects missing more than 14 doses, within a visit interval of 30 days (with exception of treatment interruptions due to toxicity (see Section 5.4.3.1)).

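### The per-protocol missed-dose rule exempts toxicity for everolimus but not for PRRT, and leaves open whether doses lost to progression or death count as missed

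*SAP*

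**What the plan says.** SAP 6.2 gives a list of deviations leading to PP exclusion and presents it as a minimum.

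- **PRRT arm:** besides incomplete infusion, "Subjects missing more than two scheduled doses, or in whom doses were administered more than 30 days outside the date, specified per protocol". Protocol 9.3.3.2 has the same rule: "Subjects missing more than two scheduled doses, or in whom dose were administered more than 30 days outside the date, specified per protocol". Neither carries an exemption.
- **Everolimus arm:** "Subjects missing more than 14 doses, within a visit interval of 30 days (with exception of treatment interruptions due to toxicity", followed by a cross-reference. Progression and death are not named.
- **Protocol 5.7** also defines the PP exclusions, but for PRRT it has only incomplete infusion and the timing criterion, "Subjects in whom a dose was administered more than 30 days outside the per protocol date". The missed-dose criterion is absent.

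The treatment rules bear on what counts as missed. The protocol synopsis plans "Four single doses administered on days 0, 90, 180 and 270, unless diagnosis of progression or EOS", and SAP 3.1 likewise runs the cycles only until progression. Protocol 5.4.1 says that PRRT patients "experiencing progressive disease under treatment must stop study participation". Sections 5.4.1.1 (kidney dose), 5.4.1.2 (eligibility after cycle 1) and 5.4.3.2 (dose-modifying toxicity) can each withhold a later cycle. Under 5.4.3.2 a patient whose toxicity has not recovered by week 16 gets no further cycles but stays in the study. The same section handles toxicity "by delaying the next treatment cycle up to a maximum of 4 weeks (week 16 (+ 2", where the unit of the final figure is not given.

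SAP 5.2.1 places the confirmatory analyses on the FAS. SAP 5.2.2 gives the PP set the job of showing whether untreated or lost patients bias the FAS result.

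**The concern.** Dose 2 is due at day 90, the same visit as the first follow-up scan. Any PRRT patient who stops before dose 2 has had at most one of four doses and meets the missed-dose criterion, whatever the reason. The everolimus criterion counts tablets within a 30-day visit interval and excuses toxicity, so a patient who took the drug daily and progressed at the month-3 scan has normally missed nothing.

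The PP set would then select on tolerability in one arm and, on a literal reading, on early outcome in that arm too. Both depend on what happened after randomisation. An analysis meant to detect bias in the FAS result would carry a bias of its own, and in the outcome case it would favour PRRT.

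**Working it through.** **1. Who meets the missed-dose criterion.** Four doses minus more than two missed leaves none or one. Patients who fail after two doses stay in the PP set.

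**2. Protocol-mandated stops after cycle 1.** On the written rule these patients are excluded, whichever way progression is read. The documents give no rate for such stops, so the effect cannot be sized; each 1% of the PRRT arm is 2 of 200 patients. The eligibility and toxicity rules are the main route. Protocol 3.4 quotes a kidney dose of 0.3–1.6 mGy/MBq (mean 0.6). Two cycles of 7.5 GBq then give at most 15 × 1.6 = 24 Gy, so the 23 Gy threshold is passed at cycle 2 only at the very top of that range.

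**3. Design figures used.** SAP section 4 states 80% power from 180 events, hazard ratio 11/17 = 0.647, 1:2 allocation, two-sided 5%. Check: Φ(√(180 × 1/3 × 2/3) × |ln 0.647| − 1.96) = Φ(6.325 × 0.435 − 1.96) = Φ(0.793) = 0.786. This agrees closely enough to use the plan's medians below.

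**4. PRRT patients with an event by day 90.** Under exponential PFS, P = 1 − exp(−ln 2 × t / median), with t = 90/30.4375 = 2.96 months. These are the patients removed if doses lost to progression or death count as missed.

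**5. Effect on the PP hazard ratio under that reading.** Simulation of 2,000 trials: 200 versus 100 patients, 30 months' follow-up, 3-monthly scans, 15% dropout, everolimus median 11 months. Only PRRT patients with an event by month 3 are removed.

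| PRRT median (months) | P(event by day 90) | Of 200 | FAS HR | PP HR |
|---|---|---|---|---|
| 11 (no effect) | 17.0% | 34 | 1.00 | 0.80 |
| 17 | 11.4% | 23 | 0.67 | 0.54 |
| 22 | 8.9% | 18 | 0.52 | 0.43 |

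A separate simulation of 1,500 trials with the same removal rule gave 1.01 to 0.81, 0.646 to 0.529 and 0.495 to 0.409. With no true effect, the log-rank test favoured PRRT at one-sided 2.5% in 39% of PP analyses (36% in the separate simulation), against 2.6% in the FAS. If doses lost to progression or death do not count as missed, nobody is removed on this ground and the PP result equals the FAS result.

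**6. Late-dose criterion.** Week 16 is day 112, which is 22 days after day 90. If the added 2 means days, the limit is day 114, 24 days late. If it means weeks, it is day 126, 36 days late and beyond the 30-day criterion. Protocol 5.4.3.2 times later cycles from the delayed one, whereas section 7.3.5 counts the month-6 visit from day 0. Dose 2 at day 112 plus a permitted 104-day interval gives dose 3 at day 216, which is 36 days past day 180 if dates run from day 0.

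**The case against.** A reader might infer that the written rule plainly removes early PRRT failures and keeps all everolimus failures, and that the PP analysis will therefore appear to confirm superiority. The documents do not support this.

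- **Progression.** The synopsis and SAP 3.1 end the dose schedule at progression, so later doses are arguably not scheduled and cannot be missed. A patient who stops as protocol 5.4.1 requires is compliant. This stands as a reasonable reading, but no passage applies it to the PP rule.
- **Everolimus.** Its rule names neither progression nor death. If doses after an event count in one arm, consistency says they count in both: an everolimus patient who dies on day 40 misses about 20 doses by day 60. This also stands in part. The figures in step 5 assume one-sided removal. That is more natural for progression found at a scheduled scan, because the patient then leaves with no later visit interval, than for death between visits.
- **Late doses.** The delay is capped at 4 weeks (28 days), later cycles are re-timed from the delayed one, and day 126 is only 22 days beyond the upper end of the day 90 (±14) window. A conflict arises only on particular readings, and this criterion does not remove patients for progressing or dying.
- **Later decisions.** SAP 6.2 refers exclusions to a Protocol Deviation Plan and blind data review. That plan is not available here. Since SAP 6.2 sets its list as a minimum, the plan is placed to add exclusions rather than to waive these.

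None of this answers the toxicity point. A PRRT patient stopped after cycle 1 for unresolved toxicity has not progressed, remains in the study and contributes PFS, yet is excluded.

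**Conclusion.** The concern holds in limited form. The toxicity asymmetry is in the text and does not depend on how progression is read; its size cannot be derived from the documents. The treatment of doses lost to progression or death is unresolved. On the literal, one-sided reading, 9–17% of PRRT patients leave the PP set at medians of 22 down to 11 months, and the PP hazard ratio falls to about 0.80 under no effect, or to about 0.53–0.54 at 17 versus 11 months. Those figures rest on exponential PFS, on local progression (which stops dosing) agreeing with central progression (which defines PFS), and on no other PP exclusions. On the other reading this shift is nil.

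Only the supportive PP analysis is at stake. It can mislead as a check on the FAS result, but it cannot rescue a failed FAS test. The point should be settled before analysis but does not threaten the primary conclusion.

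**What to change.** In SAP 6.2 and protocol 9.3.3.2, state in parallel for both arms that doses not given or delayed because of progression, death, or a stopping or delay rule of the protocol do not count as missed or late. Carry the same wording into the Protocol Deviation Plan.

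Reconcile protocol 5.7, which lacks the missed-dose criterion. State the unit of the tolerance after week 16, and define the protocol-specified date of a dose that follows a permitted delay. Correct two cross-references in SAP 6.2: it cites protocol 9.3.2 for a rule that stands in 9.3.3.2, and 5.4.2 for toxicity where the protocol cites 5.4.3.1.

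The cost is wording, and a few more PRRT patients stay in the PP set. No change to treatment rules or to the primary analysis is implied.
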